Screen prior to first chemotherapy: Approximately **1600** breast cancer patients scheduled to receive a chemotherapy regimen that contains doxorubicin, and/or cyclophosphamide, and/or carboplatin provided on a single day and an antiemetic regimen using the antiemetics recommended in the ASCO Clinical Practice Guidelines.

Prior to first chemotherapy: Informed consent, Eligibility Checklist, Participant Information, FACT-G, Medical Symptom Checklist, On-Study Form, Current Prescription Medications, blood draw for biomarker/genetic assessments

First Chemotherapy Cycle

Post-treatment assessments: Four-day Home Record (nausea and vomiting), MASCC Antiemesis Tool (MAT), FACT-G, Medical Symptom Checklist,

If nausea ≥ 3 (on a 1-7 scale)

If nausea < 3 , participant is off study

RANDOMIZED PORTION OF CLINICAL TRIAL

Stratify by NCORP site, vomiting (yes, no), setting (neo-adjuvant, adjuvant or metastatic) and whether participant is receiving a doxorubicin-based chemotherapy

R
a
n
d
o
m
i
z
e

Arm 1

Day 1: One 300mg capsule netupitant/palonosetron approximately 1 hour prior to chemotherapy + dexamethasone 12mg PO 30 minutes prior to chemotherapy + placebo¹ + placebo² q8h
Days 2 - 4: (Dexamethasone 8mg + placebo¹) qam + placebo² q8h

Arm 2

Day 1: One 300mg capsule netupitant/palonosetron approximately 1 hour prior to chemotherapy + dexamethasone 12mg PO 30 minutes prior to chemotherapy + placebo¹ + prochlorperazine 10mg q8h
Days 2 - 4: (Dexamethasone 8mg + placebo¹) qam + prochlorperazine 10mg q8h

Arm 3

Day 1: One 300mg capsule netupitant/palonosetron approximately 1 hour prior to chemotherapy + dexamethasone 12mg PO 30 minutes prior to chemotherapy + olanzapine 10mg + placebo² q8h
Days 2 - 4: (Dexamethasone 8mg + olanzapine) qam 10mg + placebo² q8h

Second Chemo- therapy Cycle

Post-treatment assessments: 4-Day Home Record, MAT, FACT-G, Medical Symptom Checklist

Note: Placebo¹ matches olanzapine and placebo² matches prochlorperazine.

TABLE OF CONTENTS

INSIDE COVER PAGE.....	Error! Bookmark not defined.
SCHEMA	3
1. INTRODUCTION AND BACKGROUND	6
1.1 Rationale	6
1.2 Literature Review and Preliminary Studies	8
1.3 Study Medications	9
1.4 Feasibility.....	9
2. AIMS/OBJECTIVES.....	9
3. CHARACTERISTICS OF STUDY POPULATION	10
3.1 Inclusion Criteria for Participation in the Cycle 1 Portion of the Study.....	10
3.2 Additional Inclusion Criteria for Participants Advancing to the Cycle 2 Portion of the Study.....	11

1. INTRODUCTION AND BACKGROUND

1.1 Rationale

Chemotherapy-Induced Nausea Remains a Significant Problem: Despite the provision of antiemetic regimens in accordance with the American Society of Clinical Oncology (ASCO) guidelines,(1) chemotherapy-related nausea remains a significant issue and is rated by patients as a greater problem than vomiting.(2-8) Nausea following chemotherapy is also three times more likely to occur than vomiting.(9) The three major antiemetic guidelines focus almost exclusively on vomiting or on nausea and vomiting combined.(1,10,11) There is little information provided specifically for nausea control and an absence of clear guidelines on which antiemetic regimen to give patients who have already experienced nausea at a prior chemotherapy cycle.

Nausea remains one of the most troublesome and frequent side effects associated with cancer treatment.(2-5,12-17) It is a widespread problem that causes extreme discomfort and seriously impairs QOL,(18,19) and it negatively affects patients' nutritional habits, ability to work, and motivation to follow recommended treatment regimens.(18-21) The introduction of the 5-HT₃ RA class of antiemetics (e.g., granisetron) more than 15 years ago reduced treatment-related vomiting, but not treatment-related nausea.(2,3,13-15) More recently, the use of palonosetron (Aloxi), a second-generation 5-HT₃ RA, and aprepitant (Emend®), a neurokinin-1 receptor antagonist, have further increased control of emesis; treatment-related nausea, however, remains a significant problem.(4,6,7,17,22,23) Our recently completed multi-center antiemetic study on optimal treatment for nausea conducted by the URCC CCOP (now NCORP) Research Base showed that nausea remains a significant problem and that more effective regimens for controlling nausea are needed.(9) Over half the patients studied experienced nausea, and control afforded by all of the antiemetic regimens examined was inadequate.

Current ASCO guidelines for refractory chemotherapy-induced nausea and vomiting (CINV) suggest that oncologists consider adding olanzapine (Zyprexa®) or a dopamine antagonist such as prochlorperazine (Compazine®) to the antiemetic regimen, but these are only two of many possible strategies for control of refractory CINV.(1) We chose to examine the efficacy of prochlorperazine in the present proposal because it is suggested for control of refractory CINV in both the ASCO(1) and National Comprehensive Cancer Network (NCCN)(11) antiemetic guidelines and because of our very positive experience with it in Preliminary Studies 1 and 2, described later. We chose to study olanzapine because it too is suggested for control of refractory CINV in both the ASCO and NCCN antiemetic guidelines and also because of the positive findings from the recently closed Alliance Group study of olanzapine for the prevention of CINV(24) and also the very positive systematic review of six randomized clinical trials evaluating olanzapine for CINV.(25)

Current Multinational Association for Supportive Care in Cancer (MASCC) guidelines do not discuss optimal treatments for nausea in patients with nausea following a previous cycle and do not recommend any specific treatment for recurrent emesis, although they do say that "rotation of antiemetics within a given family of antiemetic agents would be unlikely to lead to additional benefit."(10) ASCO guidelines for refractory vomiting suggest that clinicians should consider adding lorazepam, alprazolam, a dopamine antagonist or olanzapine to the regimen or substituting high-dose intravenous metoclopramide for the 5-HT₃ antagonist.(1) The current protocol represents a rigorous examination of the benefits of incorporating either olanzapine or a dopamine antagonist (i.e., prochlorperazine) to the Cycle 2 antiemetic regimen of patients who experienced emesis or nausea despite optimal prophylaxis at Cycle 1.

In addition, this study will provide important data on factors related to the occurrence of nausea and on optimal control of nausea in breast cancer patients receiving moderately or highly emetogenic chemotherapy. As we move to an age of more patient-centered medicine, it is easy

to see how individualized treatment regimens based on patient characteristics will enable oncologists to pick the appropriate antiemetic regimen for their individual patients, and the nausea algorithm we seek to develop could lead to a more personalized medicine by providing the information necessary for modifying antiemetic regimens based upon individual risk factors. This algorithm could lead to an empirically based personalized medical approach for control of chemotherapy-induced nausea.

Approach: The study consists of two parts with screening and some assessments occurring at baseline and chemotherapy Cycle 1 and the randomized portion of the study (N = 333) occurring at Cycle 2. During Cycle 1, we will screen and consent chemotherapy naïve breast cancer patients about to begin a chemotherapy regimen that contains doxorubicin, and/or cyclophosphamide, and/or carboplatin. All three of the drugs are commonly given and all have at least moderate emetogenic potential. A key inclusion criterion will be that all patients must be scheduled to receive antiemetic drugs recommended in the ASCO guidelines.(1) We anticipate needing to screen approximately 1600 patients, or more if necessary, to meet our Cycle 2 target number. The Cycle 2 portion will be conducted in those participants who experience moderate or greater nausea at Cycle 1 despite the recommended antiemetics prescribed at Cycle 1. It will be a Phase III randomized, double-blinded, placebo-controlled, 3-arm study (N = 333) that builds upon our prior CINV studies and investigates optimal control of CINV in patients who experienced CINV following initial chemotherapy. At Cycle 1, all rescue medications will be allowed for uncontrolled chemotherapy-induced nausea and vomiting (CINV). At Cycle 2, only the study agents can be taken for CINV. For breakthrough nausea and vomiting at Cycle 2 all rescue medications with the exception of metoclopramide and lorazepam will be allowed. We note that these two antiemetics are not allowed because benzodiazepines and anticholinergics are excluded from the protocol. We will document the type and days when prescribed rescue medications were taken.

Design Considerations

- We include a CINV assessment, but no intervention at Cycle 1, to provide baseline information on CINV for patients who are randomized at Cycle 2. It will also allow us to assess the actual levels of CINV in breast cancer patients from moderately and highly emetogenic chemotherapy when ASCO guideline antiemetics are provided.(1)
- Arm 1 will be the control condition. In this study arm, participants will receive Akynzeo® with dexamethasone along with appropriate placebos. We note that Akynzeo® is an oral, fixed combination of an NK1 receptor antagonist (netupitant) and a 5-HT₃ receptor antagonist (palonosetron) in a single capsule. It was approved by the U.S. Food and Drug Administration to treat nausea and vomiting in patients undergoing cancer chemotherapy in October 2014 and added to the ASCO antiemetic treatment guidelines in January 2015.
- An important consideration in choosing Akynzeo® for the control condition rather than continuing with the combination of aprepitant and palonosetron that most participants would have received at Cycle 1 was to ensure that no patient would be randomized to the same medication at Cycle 2 that failed to control their CINV at Cycle 1. To ensure this, we have excluded patients receiving Akynzeo® at Cycle 1 from participating in the study. We note that while aprepitant and netupitant are both NK1 receptor antagonists, they differ significantly in that netupitant has a substantially longer half-life at approximately 80 hours than aprepitant at 9-13 hours.
- We chose to study olanzapine because it is suggested for control of refractory CINV in both the ASCO and NCCN antiemetic guidelines and also because of a recent very positive systematic review of six randomized clinical trials evaluating olanzapine for CINV(25) as well as the positive findings from the recently closed Alliance Group study of olanzapine for the prevention of

CINV.(24) We note that the latter study examined prevention of CINV at Cycle 1 of chemotherapy and not treatment of refractory CINV as we propose.

- We chose to examine the efficacy of prochlorperazine in the present proposal for four reasons: 1) because of our very positive experience with it in Preliminary Studies 1 and 2, described in Section 1.2, 2) the fact that as a dopamine antagonist, prochlorperazine employs a method of action for control of nausea that is different from those of the netupitant, palonosetron and dexamethasone, and that may be additive to those agents, 3) its more than five-decade history as a widely used and very effective antiemetic in the cancer environment, and 4) its inclusion in the current ASCO guidelines as a suggestion for treating refractory vomiting(1).
- We chose to prescribe prochlorperazine q8h rather than prn because the q8h dosing was more effective than prn dosing in preliminary study 1, and also because the NCCN antiemetic Guidelines recommend routine around-the-clock administration of antiemetics rather than PRN for refractory nausea.(11)
- We chose to extend the study medication (i.e., olanzapine/prochlorperazine), as well as dexamethasone, to include Day 4 at Cycle 2 because our data in Preliminary study 2 showed that 38.3% of breast cancer patients who experienced peak nausea of ≥ 3 (scale = 1-7) during any of days 1-3 of chemotherapy also experienced nausea at a level ≥ 3 on Day 4. We note that having a peak nausea level ≥ 3 at Cycle 1 is a key eligibility criterion for the randomized portion of the current study.
- We chose to limit eligibility to breast cancer patients to make the sample as homogeneous as possible while still keeping the study clinically meaningful. This patient group has greater nausea than most if not all other large patient groups.(26)
- We chose to collect blood at baseline on participants for exploratory analyses to further elucidate the possible relationship between glutathione metabolism and CINV(27) as well as to bank blood for exploratory analyses examining germline genetic markers that might help identify subgroups of patients at high risk for development of cancer-related or treatment-related side effects as well as subgroups most likely (or least likely) to respond to a particular antiemetic regimen.(28) We note that we are not specifying any specific genetic markers at this time, but will monitor the field closely over the next several years as we collect the samples in order to target the most relevant genetic markers when we do the analyses several years from now.
- We originally predicted 1) that approximately 40% of subjects from Cycle 1 would meet all the eligibility criteria for Cycle 2 and 2) that 90% of eligible subjects would participate in Cycle 2. While our first prediction was accurate, our second prediction was not. Our assumption was that 100% of subjects eligible for Cycle 2 would participate, but the participation rate was only approximately 63% among the first 500 subjects enrolled to Cycle 1 and meeting the Cycle 2 eligibility. Therefore, it is necessary to increase our originally planned accrual for Cycle 1 from 800 subjects to 1,200 subjects. This is necessary to meet our accrual goal of 333 subjects completing Cycle 2.

1.2 Literature Review and Preliminary Studies

Preliminary Study 1 was conducted between 2001 and 2004 in 671 chemotherapy-naïve patients receiving chemotherapy containing doxorubicin.(29) All patients were given a first generation 5-HT₃ RA antiemetic plus dexamethasone on the day of treatment (Day 1) and randomized to one of three regimens for Days 2 and 3: Group 1 – prochlorperazine 10 mg p.o. every 8 hours; Group 2 – any first generation 5-HT₃ RA using standard dosage; or Group 3 – prochlorperazine 10 mg p.o. as needed. No corticosteroids were given on Days 2 and 3 of treatment. The study was

designed to determine if a 5-HT₃ RA antiemetic was more effective than prochlorperazine in controlling DN. There was no difference between the groups in mean or maximum delayed nausea (DN) severity. Patients taking prochlorperazine regularly were least likely to report DN (71% vs. 79% [Group 2] and 82% [Group 3], p<0.05).

Preliminary Study 2 tested four antiemetic regimens for control of DN following chemotherapy containing a platinum-based drug or an anthracycline in 1021 chemotherapy-naïve patients and was conducted from 2007 to 2010.(9) Group 1 of the prior study was included as a comparator group, and new groups to examine regimens containing palonosetron, aprepitant, and/or dexamethasone were added. We found that the addition of dexamethasone on Days 2 and 3 reduced DN and the beneficial effect of adding aprepitant for control of DN was the same as adding prochlorperazine.

1.3 Study Medications

The following two antiemetic medications are provided to some randomized participants during Cycle 2: Prochlorperazine (Compazine®), Olanzapine (Zyprexa®). Details on the medications are provided in Sections 5.4 and 8.

1.4 Feasibility

A key advantage to conducting this study within the NCORP network is the demonstrated track record of this group in recruiting patients prior to initial chemotherapy as evidenced by both Preliminary Studies 1 and 2 meeting their accrual goals. Other relevant factors related to NCORP are: 1) NCORP Community Sites and Minority/Underserved Community Sites have been involved in developing this protocol, 2) Interest was high with our NCORP affiliates as determined by discussion at our annual NCORP Research Base meeting in September 2015, 3) all accrual will take place at NCORP sites, and 4) the University of Rochester NCORP (previously URCC CCOP) Research Base has conducted five previous chemotherapy-induced nausea and vomiting (CINV) studies (total N = 3,365), all of which met their accrual targets.

2. AIMS/OBJECTIVES

2.1 Primary Aim is to determine if control of nausea at Cycle 2 in participants who experienced CINV at Cycle 1 is improved by the addition of either prochlorperazine or olanzapine to the control arm of netupitant, palonosetron and dexamethasone.

2.1.1 Hypothesis 1: Control of nausea at Cycle 2 in participants who experienced CINV at Cycle 1 despite receiving an ASCO-recommended antiemetics(1) can be improved by the addition of either prochlorperazine or olanzapine to the standard antiemetic combination of netupitant, palonosetron and dexamethasone.

2.2 Secondary Aim 1 is to determine if olanzapine is more effective than prochlorperazine in controlling nausea at Cycle 2 in participants who experienced CINV at Cycle 1 when used in combination with netupitant, palonosetron and dexamethasone.

2.2.1 Hypothesis 2: Olanzapine, which is a newer antiemetic drug with a more problematic side-effect profile than prochlorperazine, is more effective than prochlorperazine in controlling nausea when used in combination with netupitant, palonosetron and dexamethasone.

2.3 Secondary Aim 2 is to determine if control of vomiting at Cycle 2 in participants who experienced CINV at Cycle 1 is improved by the addition of either prochlorperazine or olanzapine to the control arm of netupitant, palonosetron and dexamethasone.

2.3.1 Hypothesis 3: Control of **vomiting** at Cycle 2 in participants who experienced CINV at Cycle 1 despite receiving an ASCO-recommended antiemetic regimen(1) can be improved by the addition of either prochlorperazine or olanzapine to the standard antiemetic combination of netupitant, palonosetron and dexamethasone.

2.4 Secondary Aim 3 is to determine if olanzapine is more effective than prochlorperazine in controlling vomiting at Cycle 2 in participants who experienced CINV at Cycle 1 when used in combination with netupitant, palonosetron and dexamethasone.

2.4.1 Hypothesis 4: Olanzapine, which is a newer antiemetic drug with a more problematic side-effect profile than prochlorperazine, is more effective than prochlorperazine in controlling **vomiting** when used in combination with netupitant, palonosetron and dexamethasone.

2.5 Exploratory Aim 1 is to create an empirically-based algorithm predicting nausea from breast cancer chemotherapy regimens that takes into account not only state-of-the-art antiemetic regimens but also participant factors such as age, race, education, ethnicity, QOL, alcohol consumption, susceptibility to nausea, expectancy, anxiety, level of nausea on the day prior to treatment, and prior history of nausea.

2.6 Exploratory Aim 2 is to compare the effects of the interventions on QOL, as assessed by the FACT-G, by following the same procedures described under the Primary Aim and the first Secondary Aim, using change in the FACT-G scores as the response.

2.7 Exploratory Aim 3 is to provide preliminary data on the frequency and severity of sleep disturbance, fatigue, anxiety, and dizziness, across treatment conditions.

2.8 Exploratory Aim 4 is to provide preliminary data on biological factors (e.g. GSH recycling, genetic markers) that may help identify a subgroup of participants at high risk for development of cancer-related or treatment-related side effects, or response to treatment.

3. CHARACTERISTICS OF STUDY POPULATION

3.1 Inclusion Criteria for Participation in the Cycle 1 Portion of the Study

Participants must:

3.1.1 Have a diagnosis of breast cancer and be chemotherapy naïve. Note: Prior methotrexate for non-cancerous conditions is allowed.

3.1.2 Be scheduled to receive a **single-day** chemotherapy regimen that contains doxorubicin, and/or cyclophosphamide, and/or carboplatin. Single-day chemotherapy is defined as **only one infusion or injection per cycle**. Herceptin® (trastuzumab) and other chemotherapy agents will be allowed with any of these regimens.

3.1.3 Be scheduled to receive an antiemetic regimen that does not contain Akynzeo®.

- For chemotherapy regimens with a **high emetic risk**, the antiemetic regimen must include an NK-1 antagonist receptor, a 5HT3 receptor antagonist and dexamethasone. Other antiemetics, including additional dexamethasone and olanzapine, may also be included at cycle one.
- For chemotherapy regimens with a **moderate emetic risk**, the antiemetic regimen must include a 5HT3 receptor antagonist and dexamethasone. Other antiemetics, including additional dexamethasone and olanzapine, may also be included at cycle one.

- 3.1.4 Be able to read English. Materials will not be provided in Spanish because validated translations of most of the study measures are not available in Spanish, and Spanish translating capacity is not available at all affiliate sites.
- 3.1.5 Be at least 18 years of age.
- 3.1.6 Be female.
- 3.1.7 Have the ability to give written informed consent.
- 3.1.8 Have ECOG performance status of 0, 1, or 2
- 3.1.9 Note: Because the NCCN antiemetic guidelines (11) state that olanzapine should be used with caution in elderly patients, patients 80 years of age or older must have approval from an oncologist or their designee to participate in this study.
- 3.1.10 Note: Because aprepitant can lower International Normalized Ratio (INR) levels if taken concurrently with warfarin, patients currently receiving warfarin must have approval from an oncologist or their designee to participate in this study.

3.1.11 Women of child-bearing potential must agree to use adequate contraception (hormonal or barrier method of birth control, or abstinence) for the duration of the study and have a negative pregnancy test within 10 days prior to the initiation of chemotherapy. Should a woman become pregnant or suspect she is pregnant while participating in this study, she should inform her study physician immediately.

3.2 Additional Inclusion Criteria only for the Participants Advancing to the Cycle 2 Portion of the Study

Participants must:

3.2.1 Only participants with a nausea score ≥ 3 at least once on the 4-day home record from Cycle 1 can be randomized for Cycle 2.

3.2.2 Participants must be scheduled to receive the same chemotherapy regimen as received at Cycle 1.

3.2.3 Because quinolone antibiotic therapy can increase the level or effect of olanzapine by altering drug metabolism and thereby potentially increase risk of side effects, patients currently receiving quinolone antibiotic therapy must have approval from an oncologist or their designee to participate in the Cycle 2 portion of the study. (A partial list of quinolone antibiotics is included in the supporting documents section of the protocol webpage.)

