3.3 Exclusion Criteria for Participation in the Cycle 1 Portion of the Study

Participants must not:

3.3.1 Have clinical evidence of current or impending bowel obstruction.

3.3.2 Have a known history of central nervous system disease (e.g., brain metastases or a seizure disorder.)

3.3.3 Have dementia.

3.3.4 Have uncontrolled diabetes mellitus or uncontrolled hyperglycemia.

3.3.5 Have severe hepatic impairment, severe renal impairment, or end-stage renal disease as determined by the treating physician.

3.3.6 Have had long-term treatment (> 5 days within the past 30 days) with an antipsychotic agent such as risperidone, quetiapine, clozapine, a phenothiazine, or a butyrophenone within 30 days before enrollment or plans for such treatment during the study period. Note: Participants could have received prochlorperazine and other phenothiazines as antiemetic therapy on a short term basis (i.e., \leq 5 days). (A partial list of antipsychotic agents is included in the supporting documents section of the protocol webpage.)

3.3.7 Have a known cardiac arrhythmia, uncontrolled congestive heart failure, or acute myocardial infarction within the previous 6 months.

3.3.8 Be taking benzodiazepines regularly (> 5 days within the past 30 days). PRN use (\leq 5 days) for the short-term relief of the symptoms of anxiety, anxiety associated with depressive symptoms, or as a rescue medication for breakthrough CINV is allowed. (A partial list of benzodiazepines is included in the supporting documents section of the protocol webpage.)

3.3.9 Be taking anticholinergic medications. (A partial list of anticholinergic medications is included in the supporting documents section of the protocol webpage.)

3.3.10 Be taking amifostine (Ethiofos).

3.3.11 Have a known hypersensitivity to olanzapine or to phenothiazines.

3.4 Additional Exclusion Criteria only for the Participants Advancing to the Cycle 2 Portion of the Study

Participants:

3.4.1 Must not have received Akynzeo® at Cycle 1.

3.4.2 Must still meet all the exclusion criteria for Cycle 1.

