The study consists of two parts with screening and assessments occurring at baseline and chemotherapy Cycle 1 and the randomized portion of the study (N = 333) occurring prior to Cycle 2. During Cycle 1, we will screen and consent chemotherapy naïve breast cancer patients about to begin a chemotherapy regimen that contains doxorubicin, and/or cyclophosphamide, and/or carboplatin. All three of the drugs are commonly given and all have at least moderate emetogenic potential. A key inclusion criterion will be that all patients must be scheduled to receive antiemetic drugs recommended in the ASCO guidelines.(1).(1) We will screen approximately 1600 patients, or more if necessary, to meet our Cycle 2 target number. The Cycle 2 portion is conducted in those participants who experience moderate or greater nausea at Cycle 1. This is a Phase III randomized, double-blinded, placebo-controlled, 3-arm study (N = 333) that builds upon our prior CINV studies and investigates optimal control of CINV in patients who experienced CINV following initial chemotherapy. A blood draw is done prior to Cycle 1 to assess biomarkers.

At Cycle 1, all rescue medications with the following exceptions will be allowed for uncontrolled chemotherapy-induced nausea and vomiting (CINV). Use of lorazepam at Cycle 1 only for the short-term relief of the symptoms of anxiety, anxiety associated with depressive symptoms, or as

a rescue medication for breakthrough CINV is allowed for a maximum of 4 days. At Cycle 1, use of metoclopramide as a rescue medication is not allowed. At Cycle 2, all rescue medications with the exception of metoclopramide and lorazepam will be allowed for uncontrolled chemotherapy-induced nausea and vomiting (CINV). We note that these two antiemetics are not allowed because benzodiazepines and anticholinergics are excluded from the protocol. We will document the type and days when prescribed rescue medications were taken.

Study Measures

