13.3 Records To Be Kept

SCHEDULE OF DATA COLLECTION			
FORMS	Baseline(Pre-chemotherapy)	After Chemotherapy Cycle 1	After Chemotherapy Cycle 2 for Randomized Participants Only
COMPLETED BY PARTICIPANT			
On-Study Form ¹	X		
Functional Assessment of Cancer Therapy Scale-General (FACT-G) ¹	X	X	X
Medical Symptom Checklist ¹	X	X	X
MASCC Antiemesis Tool (MAT) ¹		X	X
Four-Day Home Record (nausea, vomiting, rescue medication use, fatigue, anxiety, dizziness, and sleep disturbance) ²		X	X
Medication Diary			X
COVID Effects	X		X
COMPLETED BY COORDINATOR			
Consent Form ³	X		
REDCap Participant Information ⁴ (must be completed immediately following registration)	X		
Eligibility Checklist ³	X	X(for Cycle 2)	
Blood Requisition Form ³	X		
REDCap Current Prescription Medications ⁴	X		
REDCap Case Summary Form ⁴	X	X	X
Randomization		X	
Chemotherapy and Supportive Care Records (copy from medical record) ³		X	X
Telephone Contact Sheet ³		X	X
REDCap Adverse Event ⁴	X	X	X
REDCap Investigational Agent Return Form ⁴			X

¹ Paper versions of these forms are available for those participants opting out of using REDCap.

² Paper version only, coordinator will enter data into REDCap at the NCORP site.

³ Paper version only, to be submitted to URCC via scanned PDF or US mail.

⁴ REDCAP version only, no paper version. SAEs will be reported through CTEP-AERs per Section 11 and 12.

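### Does allowing olanzapine or prochlorperazine at Cycle 1, with no analysis that separates prior users, undermine the Cycle 2 arm comparisons?

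*Combined protocol and SAP*

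**What the plan says.** Section 3.1.3 sets the minimum Cycle 1 antiemetics for high-risk and moderate-risk regimens and adds, for both: "Other antiemetics, including additional dexamethasone and olanzapine, may also be included at cycle one". Section 3.3.6 excludes longer antipsychotic treatment but notes: "Participants could have received prochlorperazine and other phenothiazines as antiemetic therapy on a short term basis". On Cycle 1 rescue, Section 1.1 says "At Cycle 1, all rescue medications will be allowed for uncontrolled chemotherapy-induced nausea and vomiting (CINV"), and Section 5.1 says "At Cycle 1, all rescue medications with the following exceptions will be allowed". The exceptions concern lorazepam and metoclopramide, so neither statement bars olanzapine or prochlorperazine. (The two statements differ on those other drugs and should be reconciled, but that is a separate matter.)

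For entry to Cycle 2, Section 3.4.1 requires that participants "Must not have received Akynzeo® at Cycle 1", and Section 3.4.2 applies the Cycle 1 exclusions again. Section 4.4.2 stratifies by NCORP, vomiting, doxorubicin and setting. The primary analysis (14.5.3) is a one-way ANOVA of change with arm as the only factor. Secondary Aim 1 (14.6.1) is a contrast of arm means, and the vomiting model (14.6.2) adjusts only for Cycle 1 vomiting.

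**The concern.** Entry to the randomized part requires a nausea score of at least 3 at Cycle 1. Some participants may have reached that score while taking olanzapine or prochlorperazine. For them, the active arm gives the drug again and the control arm withholds it. For everyone else, the active arm adds something new. If the two effects differ, each contrast averages them. A weak result might then hide a real benefit in participants new to the drug, and a positive result would not show where the benefit lies.

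The design rationale in Section 1.1 seems to sharpen this. It explains the choice of Akynzeo for the control arm by a wish that nobody be randomized again to a medication that had already failed her. Read broadly, that principle is not applied to the two drugs under test.

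**Working it through.** **1. What the contrast estimates.** Let f be the share of randomized participants already given the drug in question, D_new the effect in those for whom it is new, and D_exp the effect in those exposed before. Exposure and the Cycle 1 (Pre) score are both fixed before randomization, so their expected distribution is the same in every arm. The expected Pre mean cancels between arms, and

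E(contrast) = (1 − f) × D_new + f × D_exp.

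This is the average effect in the enrolled population, with the same weights in both arms. Prior use introduces no bias. If neither group has an effect, the expected contrast is zero and each test keeps its 0.025 level.

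**2. Whether this is the stated question.** Sections 2.1 and 14.5.1 ask whether adding either drug to netupitant, palonosetron and dexamethasone improves nausea control at Cycle 2. The reference is the Cycle 2 control regimen, not each participant's earlier drugs. In exposed and unexposed participants alike, the comparison is drug against placebo on the same backbone. No aim or hypothesis is limited to participants new to the drug.

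**3. The plan's power figure.** Inputs from Section 14.3: SD 0.953, pre-post correlation 0.5, 100 evaluable per arm, difference 0.48, level 0.025 (taken as two-sided).

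- SD of change = sqrt(2 × 0.953² × (1 − 0.5)) = 0.953.
- Standard error = 0.953 × sqrt(2/100) = 0.1348; 0.48 / 0.1348 = 3.56.
- Non-central t with 297 df: power 0.904. The stated 90% reproduces.

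The 0.48 is described as half a standard deviation (0.953 / 2 = 0.477). It is not an effect observed in patients new to the drug, so the power statement does not depend on f.

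**4. How far prior use could move power.** Neither f nor r = D_exp / D_new is in the documents; both are assumed here. The average effect is 0.48 × (1 − f + f × r), with the SD held at 0.953. Power for olanzapine against control:

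| r | f = 10% | f = 20% | f = 30% |
|---|---|---|---|
| 0 | 0.829 | 0.724 | 0.595 |
| 0.5 | 0.870 | 0.829 | 0.780 |
| 1 | 0.904 | 0.904 | 0.904 |
| 1.5 | 0.931 | 0.952 | 0.967 |

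Even the direction is open. A more extreme assumption, f = 50% with nothing kept, gives 0.320, but no passage supports a share of that size.

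**5. What a restricted analysis would add.** Removing exposed participants at f = 10%, 20%, 30% leaves 90, 80, 70 per arm. The 95% half-width grows from 0.265 to 0.280, 0.297, 0.318, and power for 0.48 is 0.869, 0.823, 0.764. Whether exposed participants respond differently would remain unsettled. The standard error of that difference is 0.953 × sqrt(2/(100f) + 2/(100(1 − f))) = 0.449, 0.337, 0.294, so power for a 0.48 difference at two-sided 0.05 is only 0.187, 0.295, 0.370.

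**6. The rationale in Section 1.1.** The sentence explains why Akynzeo was chosen for the control arm, and the next one names the means: excluding participants who had Akynzeo at Cycle 1. Sections 3.1.3 and 3.4.1 do exactly that. Its wording is broader than its purpose, but it sets no rule that the eligibility criteria then break.

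**The case for a change.** The best case for the concern is practical. The trial is motivated by what to add after Cycle 1 prophylaxis has failed, and a clinician will want to know whether the answer holds for a patient who has not yet had the drug. The plan offers no such estimate. The data would be at hand: Section 5.1 says "We will document the type and days when prescribed rescue medications were taken", and Section 13.3 lists the "Four-Day Home Record (nausea, vomiting, rescue medication use, fatigue, anxiety, dizziness, and sleep disturbance") and the "Chemotherapy and Supportive Care Records (copy from medical record"). Restricting on a pre-randomization characteristic keeps the comparison randomized, and specifying it before unblinding would prevent a selective choice later.

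Much of this stands. Prior use is permitted, no planned analysis separates it, and a table of Cycle 1 exposure by arm would help readers. None of it shows that the planned analysis gives a wrong answer.

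The restricted analysis also has costs. Excluding rescue users selects on a response to Cycle 1 nausea and may leave milder cases (an assumption). A different subset for each contrast breaks the identity in Section 14.6.1, where olanzapine against prochlorperazine is built from common arm means. Finally, the evidence on prochlorperazine is thinner than it looks: the note in 3.3.6 qualifies a window before enrollment, and 3.4.2 carries the bar on more than 5 days of phenothiazine treatment forward to Cycle 2. Its permission at Cycle 1 rests on the general allowance in 3.1.3 and the rescue rules.

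**Conclusion.** The concern does not hold. The plan followed as written gives unbiased contrasts for the enrolled mix, keeps its error rate, supports its 90% power figure (0.904), and answers its stated aim. Any difference in effect by Cycle 1 drug history is ordinary heterogeneity across a baseline characteristic, which a trial need not resolve to be valid. Over assumed exposed shares of 10% to 30%, power could fall to 60% or rise to 97%, and it is unchanged if exposed participants respond alike. The documents cannot place the trial within that range, so they do not show a material loss.

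This conclusion rests on exposure being fixed before randomization, which the design ensures, and on reading the addition in the aims as relative to the Cycle 2 control regimen, which is how Sections 2.1 and 14.5.1 word it. Sections 5.4 and 6.2 cannot be read in the public copy, but the statistical sections can. A subgroup estimate or a tidier sentence in Section 1.1 would be a matter of preference and would change no planned test or stated figure.
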